#### At Week 2:

Hgb will be measured to ensure there is no rapid rise following commencement of daprodustat.

- If a rapid rise is observed (>1 g in 2 weeks), the dose should be adjusted to the next lower dose step.
- If the Hgb value at Week 2 is >12.5 g/dL, daprodustat will be stopped and reintroduced at the next lower dose at a subsequent visit when the Hgb is  $\leq$ 12.0 g/dL.
- Otherwise, no change in dose is made at Study Week 2.

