### 4.4.2. Starting Dose in the Younger Age Groups:

Assuming the PBPK model predictions are appropriate and unchanged by the PK data collected and analyzed during the study in the Integrated PK Phase, the starting dosing in the younger age groups is also provided in these tables (Table 6, Table 7 and Table 8), based on the predicted scaling (ratio of adult to pediatric dose) in Table 5.

Table 6 Starting Dose of Daprodustat for ESA Non-Users

Baseline Hgb (g/dL)	Daprodustat starting dose per age group (mg, QD)			
	Adults and 12 to <18 years	6 to <12 years	2 to <6 years	3 months to <2 years
<9	4	2	1	0.5
≥9	2	1	0.5	0.25

The lowest clearance (worst case scenario) from the predictions in the respective age groups using different assumptions
of CYP2C8 ontogeny in children. Source: Table 12 GSK Document number 2019N396674\_00

214066 Protocol Amendment 02

Table 7 Starting Dose of Daprodustat in ESA Users, Not on Dialysis

Prior ESA dose at Baseline			Daprodustat starting dose per age group (mg, QD)			
Epoetins (incl	Darbepoetin	Methoxy		(ilig, C	(טאַ	
biosimilars) (convert SC to IV U/week) a	alfa (μg/4wk SC/IV) b	PEG-epoetin beta (µg/month SC/IV)c,d	Adults and 12 to <18 years	6 to <12 years	2 to <6 years	3 months to <2 years
≤2000 e	≤30	≤40	1	0.5	0.25	0.125
>2000 to <20,000	>30 to 300	>40 to 360	2	1	0.5	0.25
≥20,000	>300	>360	4	2	1	0.5

Abbreviations: PEG = polyethylene glycol, SC = subcutaneous, IV = intravenous, U = units

- a. Standard rhEPO IV dose (U/week) = 161/113 x (epoetin SC dose (units))/(frequency) [Besarab, 2002].
- Conversion of 250U:1µg (epoetin IV:darbepoetin alfa) utilized and rounded to the nearest available dose strength [Sterner, 2008].
- Conversion of 1:1.2 μg (darbepoetin alfa:methoxy PEG-epoetin beta) utilized and rounded to the nearest available dose strength [Choi, 2013].
- d. Conversion of 208 U:1 µg (epoetin IV:methoxy PEG-epoetin beta)
- e. This includes ESA users on a zero dose / dose-hold at the time of enrolment

Table 8 Starting Dose of Daprodustat in ESA Users, Undergoing Dialysis

Prior ESA dose at Baseline			Daprodustat starting dose per age group			
Epoetins (incl	Darbepoetin	Methoxy PEG-	• • • • • • • • • • • • • • • • • • • •			
biosimilars) (convert SC to IV U/week) a	alfa (μg/4wk SC/IV)⁵	epoetin beta (μg/month SC/IV) c,d	Adults and 12 to <18 years	6 to <12 years	2 to <6 years	3 months to <2 years
≤2000e	≤30	≤40	4	2	1	0.5
>2000 to <10,000	>30 to 150	>40 to 180	6	3	1.5	0.75

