## 4.5.2. Dose Adjustment Algorithm in the Younger Age Groups

A common dose adjustment algorithm will be utilized for the 3 younger age groups, see Figure 4.

Figure 4 Dose Adjustment Algorithm in the Younger Age Groups (<12 years)

Abbreviations: m = months; PBPK = physiological based pharmacokinetics; TfOS = tablets for oral suspension; y = years.

214066 Protocol Amendment 02

These dose steps (shown in Figure 4) for the 3 younger age groups are derived by applying the adult to pediatric ratio from the PBPK model to the dosing steps for adults (see Table 9) and then lining up the doses in ascending order. This is a conservative approach, and in some cases may mean a slightly smaller dose increment than the predicted to match adult exposure, e.g., a 6 to <12 year old moves between 0.5 to 0.75 to 1 mg in a common dose algorithm rather than between 0.5 to 1 mg (see Table 9). No age group has a larger step than adult equivalent titration.

Table 9 Dose Adjustment Algorithm Predicted by the PBPK Model

Age Group	Ratio pediatric to adult dose	Dose steps predicted by the PBPK model (mg QD)							
12 <18 years	1/1	1	2	4	6	8	12	16	24
6 <12 years	1/2	0.5	1	2	3	4	6	8	12
2 <6 years	1/4	0.25	0.5	1	1.5	2	3	4	6
3 months <2 years	1/8	0.125	0.25	0.5	0.75	1	1.5	2	3

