#### From Week 4 until Week 52 (end of daprodustat dosing):

The dose may increase, decrease, be temporarily interrupted or stay the same based on Hgb response as shown in Table 11.

Table 11 Dose Adjustment Based on Hgb from Week 4 Onwards

Dose adjustment	Hgb status
To the next higher dose	
 
Hgb <10.0 g/dL and is not increasing (<0.5 g/dL) compared to previous visit.         OR
 
Hgb is within the target range 10.0 to 12.0 g/dL but in the opinion of the investigator the patient is still symptomatic due to their anemia.     
 
Note: if the participant is already on the highest dose step and requires a dose increase, maintain their age-defined maximum dose and re-check Hgb in 4 weeks.
 

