#### CONFIDENTIAL

214066 Protocol Amendment 02

Dose adjustment	Hgb status
To the next lower dose	
 
If the Hgb is >12.0 but ≤12.5 g/dL.         OR
 
the Hgb increased by >2.0 g/dL in 4 weeks.         OR
 
the Hgb increased by >1.0 g/dL in 2 weeks.         Note: if the participant is already on the lowest dose step and requires a dose reduction, withhold dosing and re-check Hgb in 4 weeks, dosing should restart at the lowest dose step when the Hgb is ≤12.0 g/dL.
 

To temporarily stop	If the Hgb is >12.5 g/dL, temporarily withhold dosing and check Hgb at the next study visit in 4 weeks.  Restart at the next lower dose when the Hgb is ≤12.0 g/dL.  Note: From Week 28 if the next study visit is more than 4 weeks from date of test, schedule an extra Hgb check Visit in 4 weeks.  Note: if the participant is already on the lowest dose step at the time of the temporary stop, dosing should restart at the lowest dose step at the next study visit when the Hgb is ≤12.0 g/dL.
No change	Otherwise maintain at the same dose.

The SoA (see Section 1.3) up to Week 28 requires visits every 4 weeks, where Hgb is checked. From Week 28 until Week 52 (when daprodustat treatment ceases), an extra Hgb Visit (at Week 32, 40 or 48) should be conducted 4 weeks after the previous study visit, if any of the following apply:

- At the previous study visit:
  - o A dose change was required (see Table 11).
  - O Dosing was temporarily withheld as follows:
    - Hgb >12.5 g/dL (see Table 11), or
    - the participant was already on the lowest dose in the dose adjustment algorithm and a dose reduction was required (see Table 11 and Section 4.5).
- The following occurs and the next study visit is not due within 4 weeks and a:
  - o Moderate CYP2C8 inhibitor has been prescribed (see Section 6.8).
  - o rhEPO or analogue has been administered in error (see Section 6.8.3).
  - Hgb check performed outside of the study (routine SoC or emergency) indicates that a dose change is needed (see Table 11).
- In the opinion of the investigator, the:
  - o Participant would benefit from continued 4-weekly Hgb checks.
  - Hgb is at the upper end of the target range and waiting 8 weeks for the next Hgb check is considered too long.

In addition to the above, an unscheduled (UNS) Visit at any time during the study may be conducted if, in the opinion of the investigator, the participant would benefit from

214066 Protocol Amendment 02

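### At Week 2 a rapid haemoglobin rise calls for a step down, but non-dialysis ESA users in the first row of Table 7 already start on the lowest step

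*Protocol*

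**What the plan says.** Section 4.6 of the protocol gives Week 2 its own list of three bullets. The first covers a rapid rise: "If a rapid rise is observed (>1 g in 2 weeks), the dose should be adjusted to the next lower dose step". The second covers Hgb above 12.5 g/dL: "daprodustat will be stopped and reintroduced at the next lower dose at a subsequent visit", once Hgb is back to 12.0 g/dL or below. The third covers everyone else: "Otherwise, no change in dose is made at Study Week 2".

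From Week 4 a separate table takes over, headed "Table 11 Dose Adjustment Based on Hgb from Week 4 Onwards". It lists the same trigger, a rise of more than 1.0 g/dL in 2 weeks, among its reasons for a dose reduction, and it has a note for the boundary case: "if the participant is already on the lowest dose step and requires a dose reduction, withhold dosing and re-check Hgb in 4 weeks". A second note in that table, added by Amendment 02, says that a participant who was on the lowest step when dosing was temporarily stopped restarts on that same step.

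Starting doses are in Section 4.4. For ESA users not on dialysis, the first row of Table 7 reads "≤2000 e ≤30 ≤40 1 0.5 0.25 0.125", with the four doses running from the oldest to the youngest age group. Its footnote e adds: "This includes ESA users on a zero dose / dose-hold at the time of enrolment". The dose steps are in Table 9, where the oldest group's row reads "12 <18 years 1/1 1 2 4 6 8 12 16 24".

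**The concern.** Week 2 is the first Hgb check after daprodustat starts, and Section 4.6 says that it is there to catch a rapid rise. If a starting group is already at the bottom of its dose ladder, an order to move one step down has no target. The site and the IRT, which Section 6.1 says is programmed with the dose adjustments, then need an answer that the Week 2 text does not give.

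The protocol treats a fast rise as relevant to safety. Table 3 reports that studies of marketed rhEPO products suggested a rise of more than 1 g/dL in any 2-week period may contribute to death and serious cardiovascular events. That statement rests on rhEPO experience. The same row of Table 3 concludes that no increased cardiovascular risk relative to rhEPO has been identified for daprodustat.

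**Working it through.** No sample-size or power figure is involved. The check sets the starting doses against the dose steps, and then looks for an instruction that covers any overlap.

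**Step 1: is Table 9 internally consistent?** Each row should equal the paediatric ratio times the adult steps 1, 2, 4, 6, 8, 12, 16, 24 mg. It does in all four age groups. The lowest steps are therefore 1 × 1 = 1 mg, 1 × 1/2 = 0.5 mg, 1 × 1/4 = 0.25 mg and 1 × 1/8 = 0.125 mg.

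**Step 2: compare every starting dose with the lowest step for its age group.**

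| Source | Cells | Cells with a lower step | Cells already on the lowest step |
|---|---|---|---|
| Table 6 (ESA non-users) | 8 | 8 | 0 |
| Table 7 row 1 (1 / 0.5 / 0.25 / 0.125 mg) | 4 | 0 | 4 |
| Table 7 rows 2 and 3 | 8 | 8 | 0 |
| Table 8 (ESA users on dialysis) | 16 | 16 | 0 |
| Total | 36 | 32 | 4 |

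The gap is confined to row 1 of Table 7.

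**Step 3: how firm is it in each age group?**
- 12 to <18 years: Table 13 gives this group IR tablets at 1 to 24 mg only, so nothing lies below 1 mg.
- 3 months to <2 years: the synopsis names 0.125 mg QD equivalent as the lowest level in the study.
- 6 to <12 and 2 to <6 years: the common algorithm contains smaller doses used in younger children. Section 4.5.2 bars dosing below the age group's own limit, but those limits are confirmed by the IDMC and may be rescaled. I take them from Table 9, because Figure 4 is not reproduced in the text available.

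**Step 4: which participants are left without a workable instruction?** A rapid riser who also passes 12.5 g/dL can follow the stop bullet. The uncovered case is a rise above 1 g/dL that ends at 12.5 g/dL or less, which needs a baseline below 12.5 − 1.0 = 11.5 g/dL. ESA users may enter at 9.5 to 12.0 g/dL (Section 5.1), so the uncovered baselines run from 9.5 to just under 11.5 g/dL. From 9.5 g/dL, for example, any rise above 1.0 and up to 12.5 − 9.5 = 3.0 g/dL falls in the gap.

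**Step 5: does another passage fill the gap?**
- Table 11 has the right boundary note, but its title and introduction start it at Week 4. Its 4-week re-check also does not match the schedule, in which the visit after Week 2 is Week 4, nominally 4 − 2 = 2 weeks later.
- The PK sampling rules (Schedule of Activities footnote k and Section 8.4.1) mention a Week 2 dose hold only for Hgb above 12.5 g/dL, not for a rapid rise.
- Section 4.5 points back to Section 4.6 for Weeks 2 to 52 and adds no lowest-step rule.
- The SAP refers to the protocol for dose adjustment.

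**Step 6: the branch above 12.5 g/dL.** The stop can be carried out from any step. The Week 2 bullet and Section 7.1.3 both set the restart one step down with no exception, while the Table 11 note keeps a lowest-step participant on the same step. These three passages do not agree.

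**The case against.** The strongest reply is that this is a missing cross-reference. Table 11 handles the same trigger at the lowest step, and a sensible site would apply that note two weeks early. Backstops exist too: Hgb is checked again at Week 4 under Table 11, an unscheduled visit is allowed at any time, and the medical monitor can authorise an IRT override if a dose change is then needed. Much of this stands, and it limits the consequence. It does not supply an instruction for Week 2. Table 11 is confined by its own title, its re-check interval does not fit, and Amendment 02 shows that the sponsor thought a related lowest-step case needed explicit text.

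Four stronger readings are tempting, and the documents do not support them.
- A reader might infer that the whole Week 2 safety rule fails for this group. It does not. Above 12.5 g/dL the drug is stopped, which is the protective part. Restart comes at a later visit, where the Table 11 restart note arguably applies. Someone entering at 12.0 g/dL who rises just over 0.5 g/dL falls in this branch and so does not illustrate the gap.
- A reader might infer that the rapid riser falls through to the no-change bullet. That bullet covers only those who met neither earlier trigger.
- A reader might take Table 3 as evidence of harm from rapid rises on daprodustat. It reports rhEPO studies.
- A reader might treat all four age groups as equally settled. The two middle groups depend on lower limits that the IDMC confirms.

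**Conclusion.** The point holds in a limited form. For a participant in row 1 of Table 7 whose Hgb rises by more than 1 g/dL by Week 2 and stays at or below 12.5 g/dL, the written instruction cannot be carried out, and no passage that applies at Week 2 says what happens instead. In the branch above 12.5 g/dL only the restart dose is inconsistent.

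The conclusion is firm for the oldest and youngest groups. For the middle two it assumes that the Table 9 lower limits apply as confirmed by the IDMC. It also assumes that Figures 3 and 4, which I could not see, carry no Week 2 note for the lowest step.

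The practical size is small. The number of participants in this row is not given. All enrolled participants were 12 to <18 years (SAP Section 8.1). The pharmacokinetic analysis plan filed with the SAP reports 4 adolescents in total and no restart of recruitment. Whether any of them was in this row is unknown. Any ambiguity lasts about two weeks, until the Week 4 check. It should still be corrected, because it concerns a safety rule, conflicts with the protocol's own starting-dose table and is cheap to repair.

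**What to change.** Reconcile the two Week 2 dose-change bullets in Section 4.6, and the restart sentence in Section 7.1.3, with row 1 of Table 7 and the lowest-step notes in Table 11. The Week 2 text should state what applies to a participant already on the lowest step under each trigger, when Hgb is next checked, and on what dose treatment restarts after a stop. Program the IRT to match. Which action is right is for the sponsor to decide.

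The cost is about one sentence per bullet, a matching clause in Section 7.1.3 and an IRT check, the same kind of change that Amendment 02 made to Table 11. As recruitment has ended, the useful form now is a documented statement of how the rule was interpreted in this trial, and a correction before the algorithm is used again.

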#### From Week 4 until Week 52 (end of daprodustat dosing):

The dose may increase, decrease, be temporarily interrupted or stay the same based on Hgb response as shown in Table 11.

Table 11 Dose Adjustment Based on Hgb from Week 4 Onwards

Dose adjustment	Hgb status
To the next higher dose	
 
Hgb <10.0 g/dL and is not increasing (<0.5 g/dL) compared to previous visit.         OR
 
Hgb is within the target range 10.0 to 12.0 g/dL but in the opinion of the investigator the patient is still symptomatic due to their anemia.     
 
Note: if the participant is already on the highest dose step and requires a dose increase, maintain their age-defined maximum dose and re-check Hgb in 4 weeks.
 

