## 2.3.1. Risk Assessment

## Table 3 Risk Assessment

Potential Risk of Clinical Significance	Summary of Data/Rationale for Risk	Mitigation Strategy								
Study Intervention (Daprodustat)										
Excessive erythropoiesis leading to thrombosis and/or tissue ischemia	In animal studies, excessive erythropoiesis (Hgb/hematocrit > upper limit normal) attributed to daprodustat was associated with vascular congestion, microthrombi, and tissue ischemia in a number of organs.  In the Phase 2 proof of concept study, a high incidence of discontinuation due to Hgb stopping criteria (Hgb >13.5 g/dL or Hgb increased >1 g/dL over any 2-week period) was observed. In non-dialysis (ND) participants administered 10 mg, 25 mg, 50 mg or 100 mg of daprodustat daily, a total of 21 of 61 participants (34%) met these criteria. In hemodialysis (HD) dependent participants administered either 10 mg or 25 mg of daprodustat daily, a total of 8 of 31 participants (26%) met these criteria.  Phase 2 dose-ranging studies and associated statistical and dose response modelling has informed Phase 3 dose rationale, starting doses, dose steps, and dose adjustment scheme to optimize Hgb management.  Integrated AE data including 2 global Phase 3 cardiovascular outcomes studies (200807/ASCEND-D and 200808/ASCEND-ND): Few participants experienced a possible thrombosis-related AE in the setting of excessive erythropoiesis (25/3419 [0.7%] participants on daprodustat vs. 14/3407 [0.4%] on rhEPO; relative risk [RR] 1.78 [0.93,3.42]) a .  Following review of clinical data received to date, erythropoiesis has not been identified as a safety concern for daprodustat when dose is managed appropriately according to target Hgb.	
 
Specific eligibility criteria related to Hgb requirements for entry are detailed in Section 5.
 
Hgb will be closely monitored throughout the dosing period as outlined in Section 4.6.
 
Specific guidance for dose adjustment or temporary discontinuation of daprodustat based on measured Hgb is provided in Section 4.6 and Section 7.1.3 respectively.
 
Monitoring of emerging safety data by an internal GSK Safety Review Team and an IDMC. The IDMC will be provided with safety data at the IDMC decision time points described in Section 9.4.1.
 
								

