Drug-drug interactions	Daprodustat is a substrate of CYP2C8. Co-administration of daprodustat with the strong CYP2C8 inhibitor, gemfibrozil increased the maximum plasma concentration (C max ) and area under the curve (AUC) of daprodustat, 4- and 19-fold, respectively, while co-administration of the weak inhibitor, trimethoprim increased the C max and AUC of daprodustat by 1.3- and 1.5-fold, respectively.  Population PK analysis from completed Phase 2 studies suggests that co-administration of daprodustat with a moderate CYP2C8 inhibitor (clopidogrel) leads to a ~2-fold increase in AUC, with no clinically significant increase in the measured Hgb response. Although CYP2C8 induction studies were not performed, co-administration of daprodustat with an inducer of CYP2C8 (e.g., rifampin/rifampicin) may decrease the exposure of daprodustat.	
 
Co-administration of daprodustat with strong CYP2C8 inhibitors, (e.g., gemfibrozil) and inducers, (e.g., rifampin/rifampicin) is not permitted as outlined in Section 5.2 and Section 6.8.1.
 
Specific guidance on the management of potential drug-drug interactions and concomitant medications is provided in Section 6.8 and Section 7.1.
 

214066 Protocol Amendment 02

Potential Risk of Clinical Significance	Summary of Data/Rationale for Risk	Mitigation Strategy
Death, myocardial infarction (MI), stroke, heart failure (HF), thromboembolic events, thrombosis of	Marketed rhEPO/ESAs have been associated with an increased risk for death and serious cardiovascular events when used in patients with anemia of CKD. Clinical studies with marketed rhEPO/analogues have suggested "higher" target Hgb, rate of Hgb rise of greater than 1 g/dL in any 2-week period, and/or higher doses may contribute to these risks.  Daprodustat has been shown to be non-inferior to ESAs in terms of first occurrence of major adverse	
 
Hgb will be closely monitored throughout the dosing period as outlined in the SoA in Section 1.3.
 
Specific guidance for (permanent or temporary) discontinuation of daprodustat based on achieved Hgb is provided in Section 7.1.
 
Monitoring of emerging safety data by an internal GSK Safety Review Team and an IDMC.
 
Specific eligibility criteria related to cardiovascular risk are outlined in Section 5.2.
 
Hgb will be closely monitored throughout the dosing period as outlined Section 4.6.
 

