vascular access at Hgb levels which are within the normal range (i.e., not polycythemic conditions)	cardiovascular events (MACE) defined as all-cause mortality, non-fatal MI and non-fatal stroke in both D patients (374/1487 [25.2%]) daprodustat vs 394/1477 [26.7%] rhEPO; hazard ratio [HR] 0.93 [0.81, 1.07]) and ND patients (378/1937 [19.5%] daprodustat vs 371/1935 [19.2%] darbepoetin; HR 1.03 [0.89, 1.19]) b .  Analysis of time to first occurrence of fatal or non-fatal thromboembolic events (deep venous thrombosis, pulmonary embolism, vascular access thrombosis) in each of the cardiovascular outcomes studies showed daprodustat did not significantly reduce the risk of fatal or non-fatal thromboembolic events compared with rhEPO in D patients (185/1487 [12.4%] daprodustat vs 215/1477 [14.6%] rhEPO; HR 0.84 [0.69, 1.02]) or ND patients (64/1937 [3.3%] daprodustat vs 51/1935 [2.6%] darbepoetin; HR 1.27 [0.88, 1.84]) b .  Analysis of time to first occurrence of fatal or non-fatal hospitalization for HF in each of the cardiovascular outcomes studies showed daprodustat did not significantly reduce the risk of hospitalization for HF (fatal or non-fatal) compared with rhEPO in D patients (112/1487 [7.5%] daprodustat vs 101/1477 [6.8%] rhEPO;	Monitoring of emerging safety data by an internal GSK Safety Review Team and an IDMC.

214066 Protocol Amendment 02

Potential Risk of Clinical Significance	Summary of Data/Rationale for Risk	Mitigation Strategy
	HR 1.10 [0.84, 1.45]) or ND patients (140/1937 [7.2%] daprodustat vs 115/1935 [5.9%] darbepoetin; HR 1.22 [0.95, 1.56]) b .  Following review of clinical data received to date, no increased risk for serious cardiovascular events relative to rhEPO has been identified for daprodustat.	

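### From Week 4, Table 11 can call for both a dose increase and a dose reduction at the same visit, and no visible text says which prevails

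*Protocol*

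**What the plan says.** Protocol Section 4.6 introduces the rules from Week 4 onward with "The dose may increase, decrease, be temporarily interrupted or stay the same based on Hgb response as shown in Table 11". The parts of Table 11 that matter here are:

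- **Increase, first criterion.** Hgb below 10.0 g/dL and up by less than 0.5 g/dL since the previous visit.
- **Increase, second criterion.** Hgb "within the target range 10.0 to 12.0 g/dL but in the opinion of the investigator the patient is still symptomatic due to their anemia". It carries no condition on the rate of rise.
- **Decrease.** Hgb above 12.0 and up to 12.5 g/dL, or a rise of more than "2.0 g/dL in 4 weeks", or a rise of more than "1.0 g/dL in 2 weeks". The two rate criteria carry no condition on Hgb level or symptoms. At the lowest step, a required decrease means withholding drug and rechecking in 4 weeks.
- **No change.** "Otherwise maintain at the same dose".

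The separate Week 2 rule, also in Section 4.6, steps the dose down after a rise above 1 g/dL in 2 weeks, stops it above 12.5 g/dL, and otherwise leaves it alone. It has no symptomatic increase, so the two instructions cannot meet at Week 2.

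Section 6.8.3 adds that after a transfusion daprodustat can continue at the current dose unless the transfusion takes Hgb above 12.0 g/dL. SAP Section 4.1 refers to the protocol for dose adjustment.

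**The concern.** The symptomatic-increase criterion and the two rate-of-rise criteria are not mutually exclusive, and they point in opposite directions. The no-change row does not settle the matter, because it applies only when no other row does. An investigator who follows the symptomatic row as printed raises the dose while Hgb is climbing fast.

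The protocol itself treats that situation with caution. The Week 2 check exists to catch a rapid rise. Table 3 records that in the Phase 2 proof-of-concept study "a high incidence of discontinuation due to Hgb stopping criteria (Hgb >13.5 g/dL or Hgb increased >1 g/dL over any 2-week period) was observed". For marketed rhEPO and its analogues, it says that a "rate of Hgb rise of greater than 1 g/dL in any 2-week period, and/or higher doses may contribute to these risks".

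The two instructions lie two dose steps apart. On the Table 9 steps for 12 to <18 years, a participant on 2 mg goes to 4 or 1 mg (fourfold apart), and one on 4 mg goes to 6 or 2 mg (threefold). From 6 to 16 mg the gap is twofold. Dose by visit and number of dose changes are secondary endpoints, so different readings at different sites would also enter those descriptive summaries.

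**Working it through.** The plan gives no figure to reproduce. The check has two parts: whether the rows overlap, and how often that might occur.

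**Overlap.** Code the rows as written on a 0.1 g/dL grid, with previous Hgb from 7.0 and current Hgb in 10.0-12.0 (21 values), symptomatic.

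- Rise >2.0 in 4 weeks: previous 7.0-7.9 gives 10 × 21 = 210 pairs; previous 8.0-9.9 gives 20 + 19 + … + 1 = 210. Total 420 pairs meet both rows.
- Rise >1.0 in 2 weeks: previous 7.0-8.9 gives 20 × 21 = 420; previous 9.0-10.9 gives 210. Total 630.
- Not symptomatic: 0 pairs.

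These counts show that the overlap exists. They are not frequencies.

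Eligible participants can reach it (Section 5.1: non-users 7.0-11.0 g/dL, ESA users 9.5-12.0 g/dL):

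- Non-user, 9.4, 9.9, 11.2 at Day 1, Week 2, Week 4: rises of 0.5 (no Week 2 cut) and then 1.3.
- ESA user, 10.0, 10.2, 11.6: rises of 0.2 and then 1.4.
- 4-week route: 8.5 to 10.8, a rise of 2.3.

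On the visit schedule the 2-week route arises only at Week 4. The 4-week route can arise at any visit 4 weeks after the last.

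**Search for a ranking.** Sections 4.5, 4.6, 6.1, 6.5 and 7.1.3 and the SAP give none. The manual IRT override in Section 4.6 is described for unscheduled visits and is not a tie-break. Section 6.8.3 covers only rises that follow a transfusion.

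**Frequency at Week 4 (illustration; the Hgb rises are assumed).** Baseline Hgb is uniform over the eligible range. Each 2-week rise is normal with mean m and SD 0.6, and the two are independent. The mean m is set so that

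P(at least one 2-week rise >1) = 1 − Φ((1 − m)/0.6)²

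equals a chosen share. Table 3 gives 21/61 = 34% and 8/31 = 26% of adults meeting the Phase 2 stopping criteria, which yields m = 0.474 and 0.348. Shares of 15% and 10% are added as assumptions. The window is Week 4 Hgb 10.0-12.0 with either rate criterion met and Week 2 Hgb not above 12.5 (4,000,000 simulated paths).

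| Share with a 2-week rise >1 g/dL | Non-users in window | ESA users in window |
|---|---|---|
| 34% | 11.1% (9.0%) | 6.0% (5.8%) |
| 26% | 7.8% (6.8%) | 5.1% (4.9%) |
| 15% (assumed) | 4.1% | – |
| 10% (assumed) | 2.6% | – |
| mean rise 0 | – | 2.4% |

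Figures in brackets set the mean Week 2-4 rise to 0 after a Week 2 cut. In the 34% non-user run, 7.55 of the 11.09 points had no Week 2 cut. With SD 0.4-0.8, recalibrated to the 34% and 26% shares, non-users span 7.4-11.3%.

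If 5-20% of those in the window are judged symptomatic (assumed):

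- Low end: 2.4% × 5% = 0.12%.
- High end: 11.1% × 20% = 2.2%.
- Per 60 planned participants: 60 × 0.12% = 0.07 to 60 × 2.2% = 1.3.
- For the 4 enrolled: at most 4 × 2.2% = 0.09.

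Later visits were not simulated.

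**The case against.** The strongest reply is that nothing compels an escalation. The lead-in is permissive, and the symptomatic criterion rests on the investigator's opinion, whereas the rate criteria are objective. Section 4.6 notes that nephrologists weigh both Hgb and clinical response. An investigator who sees a rise above 1 g/dL in 2 weeks can decline the increase. That stands: a reader might infer that Table 11 forces a dose increase during a rapid rise, and it does not. What remains is that the text does not tell the investigator to decline.

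Second, the 34% and 26% come from adults on 10, 25, 50 or 100 mg daily (non-dialysis) or 10 or 25 mg (hemodialysis), and they also count Hgb above 13.5 g/dL. ESA non-users here start at 2 or 4 mg at 12 to <18 years and lower when younger (Table 6). It would be wrong to read those shares as expected rates for this trial. The 15% and 10% rows are there for that reason.

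Third, a rule may sit in Figures 3 and 4 or in the IRT programming, which Section 6.1 says handles Hgb-based adjustment. That cannot be excluded, and the point is limited to visible text.

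Fourth, simply letting the decrease row always win would cause harm of its own. It would contradict Section 6.8.3 for transfusion-driven rises. It could also cut the dose twice for one rise: with 8.5, 9.8 and 10.6, the first rise of 1.3 triggers the Week 2 cut. The next is only 0.8, yet the total of 2.1 meets the 4-week criterion. This objection is accepted and shapes the fix.

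**Conclusion.** The point holds as a minor conflict between stated rules. From Week 4 a symptomatic participant at 10.0-12.0 g/dL can qualify for an increase and a reduction at the same visit, and the visible text does not say which applies. The missing not-rising condition, present in the first increase criterion, looks like an omission.

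The size is roughly 0.1-2.2% of participants at Week 4: about 0.1 to 1.3 per 60 planned, and under 0.1 for the 4 adolescents enrolled. This rests on assumed normal rises, on 10-34% having a 2-week rise above 1 g/dL (with a zero mean rise as the low case for ESA users), and on 5-20% judged symptomatic independently of the rise. The population PK plan issued with the SAP (Section 1.1) says recruitment would not restart, so the practical value lies mainly in any reuse of this algorithm.

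A reader might also infer a demonstrated cardiovascular hazard. The documents do not support that. The rate-of-rise statement concerns marketed rhEPO, and Table 3 concludes for daprodustat that "no increased risk for serious cardiovascular events relative to rhEPO has been identified for daprodustat". The case for change is precautionary.

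**What to change.** Add to the symptomatic-increase criterion in Table 11 that it applies only if no rate-of-rise criterion is met. No increase is then made at such a visit, and the existing decrease row applies, with two exceptions:

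1. The dose is kept unchanged, with no second reduction, if the Week 2 cut already acted on the early part of the rise and the rise since Week 2 is not above 1.0 g/dL.
2. Rises caused by transfusion follow Section 6.8.3.

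Then check the IRT logic against the revised table, and Figures 3 and 4 for any existing rule.

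The cost is a few lines of text and one logic check. The clinical downside is that a symptomatic participant waits, normally 4 weeks, for a possible increase. At the lowest step the existing Table 11 note means that drug is withheld rather than reduced. This can affect a non-dialysis participant aged 12 to <18 years who starts at 1 mg after a low or held ESA dose (Table 7). It can also affect a 2 mg starter already cut at Week 2 whose Hgb then rises by more than 1.0 g/dL.
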